8.2 Lenalidomide (Revlimid®)

In clinical trials conducted to date, lenalidomide appears to be well tolerated and has an acceptable safety profile. In Phase I/II trials of lenalidomide, the drug was well tolerated and had a manageable side effect profile. Common side effects of lenalidomide include rash, fatigue, itching, diarrhea, fever, constipation, light-headedness, and leg cramps, which generally are very mild. The most common side effects are mostly related to a drop in platelet or neutrophil counts. Severe side effects which include Stevens-Johnson's syndrome, tumor lysis syndrome, and irregular blood counts are rare. These side effects tend to be the dose limiting toxicities when attempting to achieve a full dose. The teratogenic effects of lenalidomide have not been tested in humans. However because lenalidomide is a derivative of thalidomide, all subjects are instructed to use effective contraception prior to study entry and for the duration of study participation.

Secondary Primary Malignancies

Patients treated with lenalidomide (Revlimid) may be at an increased risk of developing secondary primary malignancies than patients who were not treated with lenalidomide. Preliminary data derived from evaluation of outcomes after longer-term exposure to Lenalidomide (Revlimid) and from controlled clinical trials conducted inside and outside the United States shows an increased incidence of some second primary malignancies, particularly acute myelogenous leukemia (AML), myelodysplastic syndromes, B- cell malignancies, and Hodgkin lymphoma when compared to controls.³⁶

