11.2 Serious Adverse Events (SAE)

A serious adverse event is one that at any dose (including overdose):

- Results in death
- Is life-threatening¹
- Requires inpatient hospitalization or prolongation of existing hospitalization
- Results in persistent or significant disability or incapacity²
- Is a congenital anomaly or birth defect
- Is an important medical event³
- Suspected or positive pregnancy

¹“Life-threatening” means that the subject was at immediate risk of death at the time of the serious adverse event; it does not refer to a serious adverse event that hypothetically might have caused death if it were more severe.

²“Persistent or significant disability or incapacity” means that there is a substantial disruption of a person’s ability to carry out normal life functions.

³Medical and scientific judgment should be exercised in deciding whether expedited reporting is appropriate in situations where none of the outcomes listed above occurred. Important medical events that may not be immediately life-threatening or result in death or hospitalization but may jeopardize the patient or may require intervention to prevent one of the other outcomes listed in the definition above should also usually be considered serious. Examples of such events include allergic bronchospasm requiring intensive treatment in an emergency room or at home, blood dyscrasias or convulsions that do not result in inpatient hospitalization, or the development of drug dependency or drug abuse. A new diagnosis of cancer during the course of a treatment should be considered as medically important.

Second primary malignancies will be monitored as events of interest and must be reported as serious adverse events regardless of the treatment arm the subject is in. This includes any second primary malignancy, regardless of causal relationship to any of the study drugs, occurring at any time for the duration of the study, from the time of signing the informed consent up to the time all patients have been followed for at least 5 years from randomization or have died. Events of second primary malignancy are to be reported using the SAE report form and must be considered an “Important Medical Event” even if no other serious criteria apply; these events must also be documented in the appropriate page(s) of the CRF and subject’s source documents.

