14.2 Sample Size/Accrual Rate

To achieve 90% power to detect a 75% increase in median PFS (44.6 vs. 25.5 months), at the two-sided 0.05 significance level, will require 306 patients total, accrued over approximately 3.0 years (assuming an accrual rate of approximately 9 patients/month), with an additional 12 months of follow-up subsequent to termination of accrual.

When the sample size in each group is 153 patients, with a total number of PFS events required of 133, an exponential maximum likelihood test of equality of survival curves with a 0.05 two-sided significance level will have 90% power to detect the difference between an Arm A (Rd) median PFS of 25.5 months and an Arm B (BiRd) median PFS of 44.6 months (a constant hazard ratio of 1.75); this assumes an accrual period of 3.0 years, a maximum follow-up time of 4.0 years, and no dropouts. The exponential assumption is for planning purposes only, actual analysis will employ nonparametric methods for estimation and testing of survival distributions. Assuming a 10% dropout rate, approximately 337 patients will be accrued to the study.

A futility analysis will be conducted after 50% of the total PFS events required for final analysis has occurred (i.e., 66 of the 133 required PFS events). No accrual suspension is required to conduct the futility analysis. If at this point (i.e., after accumulation of 66 PFS events) the hazard ratio of the control arm over the experimental arm is 1.0 or less, the study will be stopped for futility.

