14.4 Analysis of Secondary Endpoints

Secondary endpoints include objective response rate (CR+PR) and complete response rate (CR) (estimated via binomial proportions), and Kaplan-Meier overall survival. Overall survival will be defined as the time from randomization day until death. Ninety-five percent confidence intervals will be calculated for the objective response proportion in each group via binomial proportions. Comparison of the objective response rate and complete response rate between the treatment groups will be performed by the chi-square test. The comparison of the overall survival distributions between the treatment groups will be performed by the log-rank test. Analysis of these three secondary endpoints will

be considered hypothesis-generating only and will be adjusted for multiplicity of outcomes by the Bonferroni method. In the event that no significant result is observed for the primary endpoint (PFS), significant findings for the secondary endpoints (even after correction for multiplicity of outcomes) will not result in efficacy claims for labeling purposes. Similarly, if a significant finding is observed for the primary endpoint, significant findings for the secondary endpoints will still not result in efficacy claims for labeling purposes. All other secondary endpoints (i.e., event-free survival, duration of response, time to progression, progression-free survival 2, and quality of life measures) will only be descriptively presented for each treatment group and no formal statistical comparison will be made between treatment arms. Confidence intervals for the secondary endpoints of objective response rate, complete response rate, and overall survival will be Bonferroni-corrected. The frequency of subjects experiencing toxicities will be tabulated. Toxicities will be assessed and graded according to CTCAE v. 4.0 terminology. Exact 95% confidence intervals around the toxicity proportions will be calculated to assess the precision of the obtained estimates.

All p-values will be two-sided with statistical significance evaluated at the 0.05 alpha level. P-values will be Bonferroni-corrected for the secondary endpoints of objective response rate, complete response rate, and overall survival. All analyses will be performed in SAS Version 9.4 (SAS Institute, Inc. Cary, NC) and Stata Version 14.0 (StataCorp, College Station, TX).

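### Second primary malignancies are collected to 5 years from randomisation in both arms, but the statistical section gives them only a crude proportion, which estimates risk at no fixed time and specifies no end-of-window analysis by arm

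*Combined protocol and SAP*

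**What the plan says.** - **Why the harm is tracked.** Section 8.2 reports: "Preliminary data derived from evaluation of outcomes after longer-term exposure to Lenalidomide (Revlimid) and from controlled clinical trials"; in its words, this evidence "shows an increased incidence of some second primary malignancies" relative to controls.
- **What is collected.** Section 11.2 makes second primary malignancies events of interest. They are reportable as serious adverse events in both arms, whatever the causality, "up to the time all patients have been followed for at least 5 years from randomization or have died".
- **When the trial is analysed.** Section 14.2 plans accrual over about 3.0 years, "with an additional 12 months of follow-up subsequent to termination of accrual". Of the power calculation it says: "this assumes an accrual period of 3.0 years, a maximum follow-up time of 4.0 years, and no dropouts".
- **How safety is analysed.** Section 14.4 says: "The frequency of subjects experiencing toxicities will be tabulated". It adds exact 95% confidence intervals for the toxicity proportions. It gives no data cut, no fixed time point, no method for unequal follow-up or death, and no analysis specific to second malignancies. These malignancies are not among the endpoints listed in section 2.2.
- **Other provisions.** Section 13.2 has the DSMB review safety and efficacy at month 6 and every six months after that, with no stated end. Section 11.3.4 requires second malignancies to be reported to the FDA, the company and the DSMB at annual renewal. Section 9.2 halts the study for review if more than 5% of patients develop one on maintenance lenalidomide, but that list still carries an unresolved drafting query about whether to include it.

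**The concern.** The protocol sets a 5-year window for this harm, and the statistical section has no method that uses it. The planned final analysis comes when the longest-followed patient has 4 years. A simple proportion at that point averages patients seen for 1 year with patients seen for 4. It also does not distinguish a patient who died early without a second cancer from one who has simply not been followed for long.

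The resulting figure would probably be read as the trial's second-malignancy risk, although it refers to no stated time. The cases for which the long window exists would have no specified place in a final comparison of the arms. Treatment continues to progression (section 4.1). If BiRd lengthens PFS as hypothesised, lenalidomide exposure could be longer on that arm, so a by-arm estimate bears on benefit and risk.

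**Working it through.** **1. Reproduce the design that fixes the analysis date.** Section 14.2 states its aim as: "To achieve 90% power to detect a 75% increase in median PFS (44.6 vs. 25.5 months), at the two-sided 0.05 significance level". It plans 153 patients per arm, "with a total number of PFS events required of 133".
- Schoenfeld events: 4 × (1.960 + 1.282)² / (ln 1.75)² = 134.2, rounded up to 135, against 133 stated.
- Exponential maximum-likelihood test, uniform accrual over 36 months, analysis at month 48: 154.2 per arm, about 309 in total, against 306 stated.
- Probability of a PFS event by month 48: 1 − [exp(−12λ) − exp(−48λ)]/(36λ), with λ = ln 2/median. This is 0.540 on Rd and 0.364 on BiRd. Expected events are 153 × 0.904 = 138. Event 133 is expected at about month 46.5 with 306 patients, or 43.1 with 337.

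The design reproduces, and month 48 is a fair date for the planned final analysis.

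**2. Set the two timelines side by side.**
- At month 48, follow-up is 48 − 36 = 12 months to 48 months, mean 30. No patient has 60 months.
- The first patient reaches 5 years at month 60 and the last at 36 + 60 = month 96.
- With no deaths, mean observation by month 96 is 78 months, so (78 − 30)/78 = 62% of it falls after month 48. Counting each patient only to 60 months, the share is (60 − 30)/60 = 50%.
- With exponential survival at a median of 36, 60 or 84 months, 45%, 51% or 54% falls after month 48. Counting only to 60 months, it is 38%, 42% or 45%. Only the 36-month median is in the documents (section 3.2, myeloma overall); 60 and 84 are assumptions.
- Section 4.2 gives 10-15 patients a month. The same 12-month rule would then put the analysis at about month 43 to 32, with 64-68% of observation after it (no deaths).

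**3. Compare the crude proportion with a 5-year risk.** The documents give no second-malignancy hazard, so h = 1% and 2% a year are assumed, constant over time. With death hazard d, cumulative incidence at t years is h/(h + d) × [1 − exp(−(h + d)t)]. The month-48 proportion is its average over t uniform on 1 to 4 years. For h = 1% and no deaths this is 1 − [exp(−0.01) − exp(−0.04)]/0.03 = 2.47%, against 1 − exp(−0.05) = 4.88%.

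| Hazard | Survival assumed | Crude, month 48 | 5-year risk | Ratio | Difference × 153 |
|---|---|---|---|---|---|
| 1%/yr | no deaths | 2.47% | 4.88% | 51% | 3.7 |
| 1%/yr | median 60 mo | 2.05% | 3.53% | 58% | 2.3 |
| 1%/yr | median 36 mo | 1.83% | 2.91% | 63% | 1.6 |
| 2%/yr | no deaths | 4.86% | 9.52% | 51% | 7.1 |
| 2%/yr | median 60 mo | 4.05% | 6.90% | 59% | 4.4 |
| 2%/yr | median 36 mo | 3.61% | 5.70% | 63% | 3.2 |

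The last column is the number of cases per arm expected after month 48 but within each patient's first 5 years.

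**4. Would running the tabulation later cure it?** At month 96 follow-up runs from 5 to 8 years. Averaging the same function over t uniform on 5 to 8 gives 6.29% against 4.88% (1%/yr, no deaths) and 3.26% against 2.91% (1%/yr, median 36 months). The crude proportion then lies above the 5-year risk. The mismatch changes direction, but the figure still belongs to no fixed time.

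**The case against.** A reader might infer that the section 14.4 tabulation is the only planned look at toxicity and that later second malignancies are never analysed. The documents do not support that. The six-monthly DSMB schedule in section 13.2 has no stated end and, if it continued through the window, would give eight further looks (months 54 to 96). Section 11.3.4 adds annual reports, and section 9.2 adds a threshold. What these provide is monitoring. None names a method for second malignancies or a final by-arm comparison, and nothing says that the DSMB reviews continue after the final PFS analysis.

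It is also fair to say that section 14.4 gives its tabulation no date. Month 48 is inferred from the only final-analysis time in the plan, and section 11.2 treats the 5-year window as part of the study, so a later tabulation is not excluded. This stands against any claim that the reported figure must cover only part of the window. It does not rescue the method, as step 4 shows.

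A further tempting inference is that late cases are where the arms will separate. That is conjecture. Both arms receive lenalidomide on the same schedule, and section 8.2 ties the risk to lenalidomide, not to clarithromycin. The comparison would also be imprecise: for an assumed 5% against 10% with 153 per arm, the standard error is √[(0.05 × 0.95 + 0.10 × 0.90)/153] = 0.030. Power at two-sided 0.05 is then about 38%. This is a good reason to keep the analysis descriptive, but not to leave the risk without a time horizon.

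Finally, the size of the gap depends on assumed hazards, and much of it simply reflects 30 months being shorter than 60. That is accepted; the figures illustrate the mismatch and are not forecasts.

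**Conclusion.** The point holds. Second primary malignancies are collected to about month 96, the planned final analysis falls at about month 48 with no patient at 5 years, and the only safety method in section 14 is a crude proportion that estimates risk at no fixed time, whenever it is run. No final by-arm analysis that adjusts for follow-up is specified.

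Run at month 48, the proportion would be about 51-63% of the 5-year cumulative incidence, with about 2 to 7 cases per arm of 153 still to come within 5 years. This rests on uniform accrual over 36 months, constant assumed hazards of 1-2% a year, and either no deaths or exponential survival with a median of 36-60 months. The timing result needs only the plan's own accrual and follow-up figures.

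This is a worthwhile and inexpensive improvement to the analysis of a recognised harm. It does not threaten the primary PFS conclusion.

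**What to change.** In section 14.4, replace the crude proportion for second primary malignancies with a cumulative incidence function from randomisation, by randomised arm, with death as a competing event and 95% confidence intervals. Report it descriptively twice:

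- at the PFS analysis, at a stated fixed time point (24 months, for example), labelled as interim for this harm;
- when the section 11.2 window closes, at 5 years, with the between-arm difference and its interval.

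Other toxicities can keep the planned tabulation. No dose, visit or stopping rule is affected.

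The cost is a paragraph in the statistical section and one further safety report about four years after the primary analysis, from data that section 11.2 already requires. The report should say that few cases are expected and that the between-arm estimate will be imprecise.

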11.3.1 Expedited reporting by investigator to Celgene

Serious adverse events (SAE) are defined in Section 11.2 above. The investigator should inform Celgene Pharmaceuticals, Inc. of any SAE within 1 business day of being aware of the event. The date of awareness should be noted on the report. This must be documented on the Onyx Therapeutics, Inc. SAE forms or a FDA 3500 or MEDWATCH form. This form must be completed and supplied to Onyx Therapeutics, Inc. within 24 hours / 1 business day at the latest on the following working day. The initial report must be as complete as possible, including details of the current illness and (serious) adverse event, and an assessment of the causal relationship between the event and the investigational product(s). Information not available at the time of the initial report (e.g., an end date for the adverse event or laboratory values received after the report) must be documented on a follow-up MEDWATCH. A final report to document resolution of the SAE is required. The Celgene protocol number should be included on the SAE reports. A copy of the fax transmission confirmation of the SAE report to Celgene should be attached to the SAE and retained with the patient records.

Celgene Drug Safety Contact Information

Celgene Corporation
Drug Safety
[name]
[name]

Toll Free: [contact]
[contact]
[contact]
Email: [contact]

11.3.2 Report of Adverse Events to the Institutional Review Board

The principal Investigator is required to notify his/her Institutional Review Board (IRB) of a serious adverse event according to institutional policy.

11.3.3 Investigator Reporting to the FDA

Adverse drug reactions that are Serious, Unlisted/Unexpected, and at least possibly associated to the drug, and that have not previously been reported in the Investigators brochure, or reference safety information document should be reported promptly to the Food and Drug Administration (FDA) in writing by [name] (the principal sponsor-investigator). A clear description of the suspected reaction should be provided along with an assessment as to whether the event is drug or disease related.

The principal sponsor-investigator shall notify the FDA by telephone or by fax of any unexpected fatal or life threatening experience associated with the use of the drug as soon as possible but no later than 7 calendar days after the sponsors initial receipt of the information. Each phone call or fax shall be transmitted to the FDA new drug review division in the Center for Drug Evaluation and Research or the product review division in the Center for Biologics Evaluation and Research that has responsibility for review of the IND.

The principal sponsor-investigator must also call the FDA as soon as an adverse reaction occurs. The phone number is [contact]. A recorder is available after hours. Report these reactions to the FDA within ten (10) working days both verbal and written.

The address of the FDA is: FDA
Division of Oncology
HFD-150
[name]
[name]

The phone number of the FDA is: [contact]

Please ask to speak with the Division of Oncology.

11.3.4 Reporting of Secondary Primary Malignancies

Secondary primary malignancies will be reported to the FDA, Celgene Pharmaceuticals, and the Weill Cornell Medical College Data Safety Monitoring Board at the time of annual renewal. Additional information regarding secondary primary malignancies listed in Section 11.2.

11.4 Adverse event updates/IND safety reports

Celgene Pharmaceuticals, Inc. shall notify the Investigator via an IND Safety Report of the following information:

- Any AE associated with the use of study drug in this study or in other studies that is both serious and unexpected.
- Any finding from tests in laboratory animals that suggests a significant risk for human subjects including reports of mutagenicity, teratogenicity, or carcinogenicity.

The Investigator shall notify his/her IRB/EC promptly of these new serious and unexpected AE(s) or significant risks to subjects.

The Investigator must keep copies of all AE information, including correspondence with Celgene and the IRB/EC, on file (see Section 15.4 for records retention information).

11.5 Provisions for Adverse Events

Necessary prophylaxis will be administered. Anti-emetics will be prescribed if necessary. Blood and platelet transfusions will be given as clinically indicated. Pamidronate or Zoledronic acid may be given monthly as part of standard care.

12.0 PROTOCOL AMENDMENTS AND DEVIATIONS

12.1 Amendments

Any amendment to this protocol must be agreed to by the Principal Investigator and reviewed by Celgene. Amendments should only be submitted to IRB/EC after consideration Celgene Pharmaceuticals, Inc. review. Written verification of IRB/EC approval will be obtained before any amendment, which affects subject safety or efficacy, is implemented. Amendments that are administrative in nature do not require IRB/EC approval but will be submitted to the IRB/EC for information purposes.

12.2 Protocol Deviations

When an emergency occurs that requires a deviation from the protocol for a subject, a deviation will be made only for that subject. A decision will be made as soon as possible to determine whether or not the subject (for whom the deviation from protocol was effected) is to continue in the study. The subject's medical records will completely describe the deviation from the protocol and state the reasons for such deviation. In addition, the Investigator will notify the IRB/EC in writing of such deviation from protocol.

Non-emergency minor deviations from the protocol will be permitted with approval of the Principal Investigator.

13.0 DATA MANAGEMENT

13.1 Analyses and Reporting

This study will be conducted at The New York Presbyterian Hospital at the Weill Cornell Medical College. Clinical data will be collected under the supervision of one of the study investigators. Clinical data will be organized and recorded with the help of data managers located at the Cornell campus. Study design and data analysis will be implemented in collaboration with our biostatistician at Weill Cornell Medical College and data will be collected and tabulated on a monthly basis.

13.2 Data Safety Monitoring Board.

The Data Safety Monitoring Board (DSMB) at Weill-Cornell Medical Center will be composed of medical and statistical independent reviewers and will meet to review the efficacy and safety data and determine a risk/benefit analysis in this subject population. The purpose of the DSMB is to advise on serious safety considerations, lack of efficacy and any other considerations within the charge to the Committee. The DSMB may request additional meetings or safety reports as deemed necessary upon discussion with Celgene and its representatives. The PI, [name], will be the safety contact for all DSMB related analysis outcomes.

[name] office is located at: NYPH-WCMC
[name]
[name]

The phone number to [name] office is: [contact]

The DSMB may stop the study following review of results from each interim analysis. The first interim analysis will take place 3 months after the study begins subject accrual or after 10 patients have been enrolled, whichever occurs first, and will examine only safety information. A subsequent interim analysis will take place 6 months after the study begins subject accrual, and every six months thereafter, and will examine both safety and efficacy. The DSMB will also review the study after 66 PFS events have occurred across both arms for futility, (as outlined in the Statistical Considerations Section 14) including toxicity data, protocol adherence, and protocol deviations and enforce stopping rules if necessary. Efficacy and safety data summaries will be provided to the DSMB after each interim analysis.

“13.3 Study Monitoring and Auditing

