9.2 Early Termination of Study

Study-terminating events are listed below (to include?):

- *Early death (defined by death within 30 days of beginning therapy) deemed to be related to study treatment of more than 1 of the first 10 subjects.*
- *Early need for hospitalization (defined by hospitalization within 30 days of beginning therapy) of more than 5 of the first 10 subjects.*
- *If there is an unacceptable rate of Grade 4 toxicities (according to CTCAE version 4.0), as deemed by the research team, Celgene, or the Data Safety Monitoring Board.*

- *If >5% of patients develop a secondary primary malignancy on maintenance lenalidomide, the study will be halted and reviewed by the Investigator and Data Safety Monitoring Board before a decision will be made to proceed.*

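### Efficacy is reviewed every six months with power to stop, but the plan neither excludes stopping for benefit nor sets a boundary, so the PFS type I error is not protected as written

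*Combined protocol and SAP*

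**What the plan says.** Section 13.2 of the combined protocol and SAP sets a first, safety-only interim analysis, then analyses from "6 months after the study begins subject accrual, and every six months thereafter, and will examine both safety and efficacy". It adds: "The DSMB may stop the study following review of results from each interim analysis". The direction of the stop is not limited. The board's purpose is to "advise on serious safety considerations, lack of efficacy and any other considerations within the charge to the Committee". A further review at 66 PFS events is for futility, "including toxicity data, protocol adherence, and protocol deviations and enforce stopping rules if necessary".

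Section 14.2 sizes the trial "at the two-sided 0.05 significance level, will require 306 patients total", "with a total number of PFS events required of 133", for 90% power. Its only interim rule is this: "A futility analysis will be conducted after 50% of the total PFS events required for final analysis has occurred". The trial stops if the hazard ratio, control over experimental, is 1.0 or less at that point. Section 14.4 judges all p-values at two-sided 0.05. Its Bonferroni correction covers three secondary endpoints and does not address repeated looks.

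Section 9.2 opens with "Study-terminating events are listed below (to include" and a question mark. The grounds it lists are all safety grounds.

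Neither section 13.2 nor section 14 gives an efficacy boundary, an interim threshold, alpha spending or an adjusted final level, or says that the trial will not stop for benefit.

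**The concern.** PFS is the single primary endpoint of an open-label phase III trial, and the two-sided 0.05 is its only protection against a false claim. That level holds for one test at 133 events. It also holds if interim efficacy reviews cannot lead to a positive stop. It does not hold automatically when a board sees efficacy several times and may stop on what it sees. The result then depends on the threshold the board applies, and these documents state none. If the trial stopped early for benefit, its error rate could not be established afterwards from the plan.

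**Working it through.** **1. The plan's own figure.** Inputs from section 14.2: hazard ratio 1.75 (44.6 vs 25.5 months), two-sided 0.05, power 90%, 1:1 allocation.

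- Events (Schoenfeld) = 4(1.960 + 1.282)² / (ln 1.75)² = 4 × 10.51 / 0.3132 = 134.2, so 135, against 133 stated.
- Power at 133 events = Φ(ln 1.75 × √133 / 2 − 1.960) = Φ(3.227 − 1.960) = Φ(1.267) = 0.897.

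The 133 events therefore correspond to one final test at the full 0.05, with nothing set aside for interim looks.

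**2. Number of looks.** With both medians at 25.5 months, 306 patients and uniform 36-month accrual, expected events at months 6, 12, 18, 24, 30 and 36 are about 4, 15, 32, 54, 81 and 111. In simulation, 133 events arrive at a median of month 40.3. Six six-monthly looks precede the final analysis in 81% of trials and seven in 19%.

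**3. False-claim rate for BiRd.** The simulation used 60,000 null trials, 153 patients per arm, exponential PFS and no dropout. Futility stopped a trial when the log-rank at event 66 did not favour BiRd. The final test was at two-sided 0.05 at event 133.

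Two inputs are assumptions, because the documents state neither: that PFS is log-rank tested at each six-monthly look (once at least 5 events have occurred), and the interim threshold. Only crossings in favour of BiRd count, so the reference value is 0.025, half of the two-sided 0.05.

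| Assumed interim threshold (two-sided p) | BiRd-side false-claim rate |
|---|---|
| No stop for benefit | 0.025 |
| 0.001 | 0.026 |
| 0.005 | 0.030 |
| 0.01 | 0.036 |
| 0.02 | 0.049 |
| 0.05 | 0.090 |

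The simulation standard error is about 0.0006 at 0.025 and 0.0012 at 0.09. At the 10 to 15 patients per month of section 4.2, the p<0.001 row is 0.025 to 0.026 and the p<0.05 row is 0.083 to 0.088, so accrual speed matters little.

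**4. How often the question would arise if BiRd works as hypothesised.** With medians of 25.5 and 44.6 months and 36-month accrual (20,000 trials), about 44% cross p<0.001 for BiRd at some six-monthly look before 133 events. A smaller run on timing gives about 8% by month 24, 16% by month 30 and 29% by month 36. About (44 − 16)/44 = 64% of crossings therefore come at the month-36 look or later, when planned accrual is complete.

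**5. Cost of a boundary.**

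- Haybittle-Peto, interim p<0.001 and final 0.048: on event counts 15, 32, 54, 81, 111 and 133 the total two-sided error is 0.0497. Power from the final test alone is Φ(3.227 − 1.977) = 0.894, and 0.895 with interim crossings.
- O'Brien-Fleming-type spending: final level about 0.036 to 0.041, power 0.883 to 0.890.

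**The case against.** The strongest reply is that no stop for benefit is intended. Where the plan wants an outcome-based stop it gives a number, and that number is for futility. The two named purposes of the board are safety and lack of efficacy. The reference to enforcing stopping rules sits in the sentence on the futility review, and section 9.2 lists only safety grounds. On that reading the false-claim rate is 0.025 and nothing is inflated.

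This makes the reading plausible but does not make it a rule. The purpose sentence continues to other considerations within the committee's charge, and the power to stop is a separate sentence covering every interim analysis. The section 9.2 list carries an open question mark and omits the futility stop that section 14.2 requires, so it is not a complete list of grounds.

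Three parts of the objection stand:

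- The charge is not in the documents and may already exclude a benefit stop. One can say only that no rule is written here.
- The documents do not name the efficacy measure at the six-monthly looks. Response rate would fit the wording as well as PFS, so every figure above 0.025 rests on an assumed PFS test as well as an assumed threshold.
- A reader might infer that the board will probably face a decision on benefit. The 44% does not support that: it is below half, holds only under the full hypothesised effect, and arises mostly late.

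**Conclusion.** The point holds as a gap in the stated design. The plan combines repeated efficacy review, an unrestricted power to stop and a single unadjusted 0.05, and says nothing that fixes the error rate of the PFS test.

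The size depends on the missing rule. On the BiRd side, against 0.025, it runs from no inflation (no benefit stop) through about 0.026 (p<0.001) and 0.036 (p<0.01) to about 0.09 if the plan's only stated level were used at every look. These are one-directional rates with futility applied and should not be compared with 0.05.

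A reader might infer that the trial's type I error is 9%, or about 0.20 counted two-sided over seven looks without the futility rule. The documents do not support that. They nowhere say that 0.05 applies at interim looks, so those are worst cases under assumption.

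Confidence is high that these documents contain neither an exclusion nor a boundary. What the board would do is unknown. It should be fixed, because it concerns the primary endpoint's error rate and the repair costs almost nothing.

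**What to change.** State in sections 13.2 and 14.2 that the six-monthly efficacy reviews inform the DSMB's risk/benefit judgement only, and that the trial will not be stopped for benefit before 133 PFS events. Alpha, events and patient numbers do not change. The board's safety, lack-of-efficacy and futility roles stay as written. If the charge already says this, repeat the sentence in section 14.2.

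If stopping for benefit is wanted, prespecify one of the following for PFS, and name the test used at each look:

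- **Haybittle-Peto:** two-sided p<0.001 at each interim look and the final at about 0.048. Power at 133 events goes from 89.7% to about 89.4 to 89.5%.
- **O'Brien-Fleming-type spending** on the fraction events/133, with the final level computed from the actual event counts (about 0.036 to 0.041). Power goes to about 88.3 to 89.0%.

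The cost in power is thus between 89.7 − 89.5 = 0.2 and 89.7 − 88.3 = 1.4 points.
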